3.1.3 Data collection

Information on exposures (depression status, and treatment), outcome (PTD & LBW), and other psychiatric disorders (comorbidity) will be ascertained through KPNC EMR data sources for all

88,000 women who have been screened for peripartum depression. Confounders not available from the KPNC EMR will be ascertained during interview of the stage-two subsample of 3,600 women (Figure 2). OBGYNS will inform all pregnant women who screen positive by PHQ-9 about our study during their prenatal visits. Table 1 describes briefly the sources and categories of factors to be ascertained.

		Universal Screening	EMR data	Interview
Depression and treatment	Depression and its severity	X	X	
	Psychotherapies	X	X	
	Antidepressant use	X	X	
	Combination therapy	X	X	
	Other psychiatric disorders		X	
Outcome	Gestational Age/PTD, LBW		X	
Potential confounders, mediators and effect modifiers	Risk factors for PTD, LBW		X	X
	History of mental illness		X	X
	Reproductive history		X	X
	Preexisting diabetes or GDM		X	X
	BMI		X	X
	History of depression	X	X	X
	Substance abuse		X	X
	Reproductive and pregnancy history		X	X
	Family and social support		X	X
	Demographic characteristics		X	X
Family history of mental illness			X	

Depression status and severity

Depression status and its severity during pregnancy will be ascertained through PHQ-9 scores from the universal depression screening and clinical diagnosis. All pregnant women who come to the first prenatal visit will be screened for depression using the PHQ-9, which has been validated in many studies as an instrument for screening for depression with high sensitivity (> 88%) and specificity (> 88%) in obstetric patients¹⁰³⁻¹⁰⁷. PHQ-9 was chosen as the screening instrument after consultation with many nationally recognized experts in the field of diagnosis and treatment of peripartum depression balancing out many factors including scientific validity and feasibility for a large scale population-based screening program. As a currently accepted cutoff, PHQ-9 scores (≥ 10) in combination with evaluation by medical practitioners will be used to determine whether a pregnant woman screens positive for depression. A score above 10 will be used as a measure of the severity of depression. Women who screen positive are referred by clinicians, under the screening protocol, to departments of

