psychiatry, psychology, or behavioral modification. Information on PHQ-9 scores, referrals, patient's uptake (or decline) of prescribed treatments are also captured by our EMRs. Any clinical diagnosis and treatment of depression for those not captured by the screening will also be identified through EMRs. During the glucola visit (22-24 weeks of gestation), all women will be screened for depression a second time using the same screening process as the first prenatal visit.

Women being treated for depression before the screening will be identified (<2%) and analyzed as a separate group.

Depression severity will also be used for stratification (to control for confounding by indication) when conducting head-to-head comparison of treatment effect among various treatment options.

Depression type (with or without other psychiatric comorbidity) will be determined by identifying concurrent psychiatric disorders from KPNC EMRs including organic psychotic conditions, other psychoses, neurotic and personality disorder and other mental disorders. The expected number of women who have depression only and depression with comorbidity during the study period is listed in Figure 2.

Antidepressant use during pregnancy. Antidepressant use, including types, timing, and duration of use, will be ascertained both through the depression screening and EMR (i.e., pharmacy database). The KPNC pharmacy database captures all inpatient and outpatient prescriptions and dispensations. Because of a large financial incentive to obtain medications at KPNC (in most cases, medications are covered with minimal co-payments), the KPNC pharmacy database has been shown to capture 93-98% of prescription medications of varying types. Compliance of taking antidepressants will also be ascertained during interview.

Psychotherapy. KPNC EMR records any psychotherapy patients receive for depression. The information includes the type of therapies (individual or group), sources of the treatment (psychologist, behavioral modification specialist, or psychologist/social worker) and number of sessions attended.

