5 COMPARATORS

Comparators will vary depending on the research questions to be examined in analyses. The overall objective is to use appropriate comparators so that correct results of comparative effectiveness can be obtained after disentangling treatment effect from the effect of underlying depression (confounding by indication), and treatment benefits after balancing treatment benefit against the simultaneous risk of side effect (e.g., use of antidepressants). The following four cohorts (A-D) will be established within each depression type (depression only or depression with comorbidity) and various comparators will be used to answer the research questions in the Specific

Aims. We will also establish a control cohort (E) of women without depression for comparison of baseline risk.

Cohort A: women who screened positive and used antidepressants only. All women who screened positive for depression and were subsequently prescribed antidepressants during pregnancy will form Cohort A. Comparison of this cohort to Cohort D, a comparator for Specific Aim 1, will demonstrate the treatment effect of antidepressant use in reducing the fetal risk after controlling for severity of depressive symptoms and other confounders. Comparisons to Cohort B or C, comparators for Specific Aim 2, will determine which treatment option (antidepressant use, psychotherapy or combination therapy) is more effective in reducing fetal risk or has a better risk-benefit profile (pair-wise comparisons). Results from such comparisons will provide valuable information for clinicians as well as pregnant women to make an informed decision on the treatment options for depression during pregnancy based on research evidence.

Cohort B: women who screened positive and received psychotherapy only. This cohort consists of women who screened positive and subsequently received psychotherapy during pregnancy, but did not take any antidepressants. Comparison to Cohort D will determine if mitigation of depression by psychotherapy reduces fetal risk, after controlling for depression severity. Comparisons of this cohort to antidepressant use (Cohort A) or combination therapy (Cohort C), two separate comparators for Specific Aim 2, will provide head-to-head assessment of comparative effectiveness of treatment regimens.

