6 ANALYTIC METHODS

6.1 General Approach to Analyses

While all eligible pregnant women will be included in the registry after their pregnancies are identified, the follow-up time for all pregnancy outcomes of interest will start at 20 weeks of gestation because, by definition, PTD and LBW among live births occur after 20 weeks of gestation. All pregnancies ending before 37 completed weeks (259 days) will be considered as failure (PTD). As in our previous studies, we will use the Cox proportional hazards regression model, accommodating delayed entry into the cohort^{76,77}. Birthweight for all newborns will be obtained from EMR and analyses for LBW will utilize logistic regression.

The study design can be characterized as two-stage. Unlike typical applications of two-stage sampling in epidemiologic studies, where the stage-two sample is selected on the basis of both exposure (or exposure surrogate) and outcome (e.g. two-stage case-control sampling), only exposure status will be known at the time of stage-two sampling to keep the nature of a cohort study design. However, study outcomes of interest will eventually be measured on all 88,000 stage-one units, and there is much to be gained by utilizing all available information in estimation of associations of interest (see Sample Size and Statistical Power section).

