We will also examine the possible dose-response in the association between antidepressant use and PTD by examining dosage of use, duration of the use, and timing of effect (single vs. multiple trimesters), in the context of time-dependent covariates. Similarly, we will also assess any dose-response relationship in the association between psychotherapy and PTD (the number of sessions received) and the effect of timing of treatment, also both as time-dependent covariates. If sample sizes allow, we will also examine the effect of combination of dose and timing (e.g., dose-response during early and late pregnancy). In addition, we will examine difference in the type of antidepressants (SSRI vs. non-SSRI).

Analyses of LBW as the outcome will parallel those described above for PTD, but logistic regression techniques will be used rather than Cox regression.

Aim 2. Head-to-head comparison of treatment regimens among Cohorts A, B & C, respectively

We will obtain point and interval estimates of relative hazards of PTD associated with the three pairwise contrasts among the three treatment groups. These estimates, and associated tests of significance, will be obtained using the Cox proportional hazards regression model developed in addressing Aim 1, fully adjusted for potential confounders including depression severity, as described above, via transformed linear contrasts of treatment group associated regression parameters. Based on the results of Aim 1 analyses of dose-response, we will obtain confounder adjusted relative hazards associated with PTD with levels of dose of a given treatment modality

(e.g. antidepressants, <30 days, 30-120 days, > 120 days duration during pregnancy), vs. particular levels of dose of another treatment (e.g. psychotherapy, ≥ 4 visits that has shown to be effective). We would categorize the comparator treatment (e.g., psychotherapy), based on the Aim 1 findings that the effectiveness of the comparator treatment in reducing risk of PTD varied by dose (e.g. no effect for < 4 visits).

As a secondary (exploratory) analysis, we will evaluate the treatment effectiveness separately for those with more severe underlying depression before treatment vs. those with more mild depression. Treating depression may be more beneficial for those with severe depression.

Analyses of LBW as the outcome will parallel those described above for PTD, but logistic regression techniques will be used rather than Cox regression.

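### The example antidepressant level of more than 120 days is empty before 37 weeks for women first identified at the 22-24 week screen, so the PTD duration contrasts are partly confounded with time of identification

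*Combined protocol and SAP*

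**What the plan says.** Section 6.1, Aim 1, examines antidepressant dosage, duration and timing in relation to PTD as time-dependent covariates. It adds a joint analysis of dose and timing if numbers permit. Aim 2 builds on those results. It gives example duration levels, "antidepressants, <30 days, 30-120 days, > 120 days duration during pregnancy", each to be contrasted "vs. particular levels of dose of another treatment (e.g. psychotherapy, ≥ 4 visits that has shown to be effective".

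Four other statements fix the time available for treatment:

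- Section 6.1, start of risk: "the follow-up time for all pregnancy outcomes of interest will start at 20 weeks of gestation".
- Section 6.1, end of risk: "All pregnancies ending before 37 completed weeks (259 days) will be considered as failure (PTD".
- Section 3.1.3, two screens: "All pregnant women who come to the first prenatal visit will be screened for depression using the PHQ-9", and "During the glucola visit (22-24 weeks of gestation), all women will be screened for depression a second time".
- Section 5, treatment follows identification: "All women who screened positive for depression and were subsequently prescribed antidepressants during pregnancy will form Cohort A". Section 3.1.3 sets earlier users apart: "Women being treated for depression before the screening will be identified (<2%) and analyzed as a separate group".

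Under Aim 1, confounders are kept or dropped by comparing adjusted with unadjusted hazard ratios. Depression severity is named for control. Gestational age at identification or at treatment start is not. The propensity model in section 6.1.1 uses the same variables as the conventional models.

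**The concern.** The duration levels are fixed day counts, but the time in which days can accumulate before 37 weeks depends on when depression was found. If the longest level cannot be reached from the second screen, it holds only women found and treated early, while the other levels and the psychotherapy comparator hold women from both screens. Should early-found and later-found depression carry different PTD risk, part of that difference would appear as an effect of treatment duration in Aim 1, and as a difference between treatments in the Aim 2 dose-level contrasts. Those results are meant to inform treatment choice.

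**Working it through.** **1. The plan's own figure.** 37 × 7 = 259 days, as section 6.1 states.

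**2. Latest start that can reach the top level.** More than 120 days means at least 121. 259 − 121 = day 138 = 19 weeks 5 days. The second screen opens at 22 × 7 = day 154, which is 16 days later.

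**3. Most days available before 37 weeks** (259 minus day of start, use every day):

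| Start | Day | Maximum days | 121 days reached at |
|---|---|---|---|
| 22w0d | 154 | 105 | 39w2d |
| 23w0d | 161 | 98 | 40w2d |
| 24w0d | 168 | 91 | 41w2d |
| 24w6d | 174 | 85 | 42w1d |

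A woman first positive at the second screen could pass 120 days only after she can no longer have a PTD.

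**4. First-visit women.** The documents give no gestational age for the first prenatal visit. For assumed starts at 8, 12 and 16 weeks the maxima are 203, 175 and 147 days, and the top level is reached at 25w2d, 29w2d and 33w2d. These women can fall in all three levels, depending on when they start and stop.

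**5. Why time-dependent coding is not enough.** It compares women at the same gestational age and so deals with immortal time. It does not put second-screen women into the top level. Four or more visits, by contrast, can be reached within 91-105 days.

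**6. Size, under stated assumptions.** Let θ be the hazard ratio for early-identified v later-identified depression, and p the share of early-identified women in the 30-120 level at a given gestational age. With no effect of duration, the apparent hazard ratio for >120 v 30-120 days at that age is

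θ / (pθ + 1 − p).

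With θ = 1.3:

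- p = 0 gives 1.30, the upper bound.
- p = 0.57 gives 1.3 / (0.741 + 0.43) = 1.11.
- p = 1 gives 1.00.

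The value of p falls late in the risk period. With continuous use, starts at 9-14 weeks pass 120 days by 31w2d (14 × 7 + 121 = 219), and starts at 23-27 weeks reach 30 days by the same point (27 × 7 + 30 = 219). After that the two levels separate entirely by time of identification.

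Simulation with no duration effect assumed 30% or 50% second-screen women, starts at 9-14 or 23-27 weeks, PTD about 9.5%, and time-updated duration with terms for gestational week:

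| Timing effect θ | Use | Spurious HR, >120 v 30-120 days |
|---|---|---|
| 1.3 | continuous | 1.17-1.27 |
| 1.3 | mean 150 days | 1.11-1.18 |
| 1/1.3 | continuous | about 0.8 |
| 1/1.3 | mean 150 days | about 0.8-0.9 |
| 1 | either | 0.99-1.02 |

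The lower end for continuous use comes from a flat weekly hazard. Second-screen women made up about 19-43% of the 30-120 person-time and none of the >120. For >120 days v four or more visits (assuming fortnightly visits), the spurious hazard ratio was 1.08-1.13, or 0.87-0.94 in reverse. Adding an indicator for screen, or restricting to first-visit women, brought the >120 v 30-120 hazard ratios back to about 0.95-1.05.

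**The case against.** The cut-points are only examples and depend on what Aim 1 shows. The plan already lists timing of exposure, time-dependent coding and a possible dose-by-timing analysis. The bias needs a prognostic effect of early v late identification, which the documents do not establish. The nearest text, in section 5 under Cohort D, compares symptoms at both visits with symptoms at one visit only. That puts women positive only at the first visit with women positive only at the second, so it supports a timing effect only indirectly. Nor do the documents give the share of women found at each screen. The three main cohort contrasts do not use these levels.

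All of this limits the size and reach of the point. It does not remove it. These are the only duration levels the plan offers, and any cut above about 105 days leaves the same empty cell. The dose-by-timing analysis is conditional, and no text ties the duration contrasts to time of identification.

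A reader might go further and infer that the contrasts compare early-identified with later-identified women in place of long with short treatment. The documents do not support that, because first-visit women can occupy every level. Nor do more days always mean an earlier start. At 30 weeks, a woman who used antidepressants from 9 to 12 weeks has 21 days, while one treated continuously from 23 weeks has 49.

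**Conclusion.** The empty cell is certain: no woman first positive at the 22-24 week screen can have more than 120 days of use before day 259. It follows that duration and time of identification are partly confounded in the follow-on PTD dose-level contrasts of Aims 1 and 2, and that nothing pre-specified removes this. The size cannot be derived from the documents. Under the assumed 30-50% second-screen share and a 1.3-fold (or 1/1.3-fold) hazard for early-identified depression, the spurious hazard ratio for >120 v 30-120 days is about 1.1-1.3 (or 0.8-0.9). It is smaller against four or more visits, and absent if timing is not prognostic. The point is limited in scope but cheap to settle in advance.

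**What to change.** In every PTD duration contrast, name gestational age at first identification as a pre-specified covariate or stratum, and do not leave it to change-in-estimate selection. Define it as the date of the first positive screen or of the clinical diagnosis, whichever identified the woman. Both are in the EMR, and this also covers women diagnosed outside screening.

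Estimate any contrast that uses the >120-day level only among women identified early enough to reach it, for example those first positive at the first prenatal visit. Apply the same restriction to the comparator. Adjustment alone can remove the bias if the duration effect does not vary with time of identification, but it extrapolates into an empty cell. Restriction avoids that extrapolation.

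Replacing duration with the share of days covered since identification would not serve, because two weeks and twenty weeks of full use would score the same.

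The cost is a few sentences in the analysis plan and one restriction in the code, with fewer women and wider intervals in the >120-day contrasts.

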6.2.2 Sample size and statistical power

We expect to measure primary exposures (depression and treatment), and outcomes of interest (PTD, LBW) in approximately 88,000 women (stage-one sample). Randomly sampling from the stage-one cohort, we expect to recruit 400 pregnant women from each cohort (see Figure 2). Given the lack of methods for power calculations for the semiparametric maximum likelihood estimator (SMLE) in our two-stage sampling scheme, we very conservatively present minimum detectable effect calculations assuming the second stage sample of 3,600, noting that the gains in precision and statistical power in utilizing the measurements in stage-one sample of 88,000 women will be significant. In a small simulation study described below, we examine efficiency gains of an ad-hoc two-stage relative hazard estimator currently under investigation, which is an alternative to the semiparametric maximum likelihood estimator, attractive in its simplicity. These results provide information on the efficiency gains that can be expected in our two-stage design with the maximum likelihood estimation; the maximum likelihood estimator will be more efficient than the ad-hoc. Given results of the preliminary simulation study, we also present below estimates of minimum detectable effects using the two-stage SMLE for most estimates (in brackets, assumptions described below). Power calculations are based on the likelihood ratio test in the context of a Cox proportional hazards regression analysis and a logistic regression analyses, as appropriate to the outcome^{89 90}.

Given previous experience^{3,91-93}, we expect negligible loss to follow-up (< 1%). Based on our experience with our study population⁹⁴, we expect a rate of PTD (gestational age < 37 weeks) ranging from 8% - 11% and LBW ranging from 5% to 10%.

Each primary contrast of interest in analyses addressing **Aims 1 through 3** can be characterized as a comparison of two groups of 400 women with respect to risk of study outcomes of interest (N=800). Minimum detectable hazard ratios for PTD range from 1.69 – 1.83 across the range in expected rate of PTD (Table 5). Minimum detectable odds ratios for LBW range from 1.67 to 2.05 across the range in expected event rate.

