Relevant to **Aim 4** analyses of heterogeneity in the association between treatment/depression and PTD by psychiatric comorbidity status (yes/no with 50% of total stage 2 sample in each of the two groups), the minimum detectable hazard ratio for effect modification (interaction) was calculated, assuming a pairwise comparison of treatment effect (e.g. A vs. D) and the midpoint of the range in expected PTD rate (9.5%) [N for analyses = 1600]. The hazard ratio for effect modification is interpreted as the factor by which exposure to the effect modifier (comorbidity status = yes) increases the hazard ratio associated with treatment, over and above that in those unexposed to the effect modifier (comorbidity status = no). Using methods as outlined above, the minimum detectable hazard ratio for effect modification is 1.50, and similarly for analyses of LBW, the minimum detectable odds ratio for effect modification is 1.62 (two-sided test, $\alpha=.05$, power =.80). While this stratification analysis is an *a priori* aim of the study with relevant clinical implications, we will be conservative in interpretation of our findings due to increased number of comparisons from stratification by depression type, though the need to adjust for multiple comparisons remains controversial⁹⁵⁻⁹⁷.

Table 4. Comparison of Maternal Age and Race/Ethnicity for Newborns between KPNC and the General Population in the KPNC Service Regions

Characteristics	KPNC Births (%)	All births in the KPNC Service Regions (%)
Maternal age		
< 20	12	10
20-29	43	52
30+	45	38
Maternal race/ethnicity		
Asian	15	16
Black	10	10

Table 5. Minimum detectable hazard ratios (HR) for preterm delivery and minimum detectable odds ratios (OR) for low birthweight in a pair-wise comparison of depression exposure/treatment categories (N=800); two-sided test, significance level (α) = .05, power (1- β) =.80.

Preterm Delivery (HR)		Low Birthweight	
Rate = 8%	Rate = 11%	Rate = 5%	Rate = 10%

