Efficiency increase resulting from two-stage study design: A preliminary simulation study has been conducted providing information on the expected efficiency gains of the two-stage SMLE, relative to an analysis of the stage-two subsample only. For our preliminary simulation study, we made a few simplifying assumptions. We assumed three depression status categories, none, depressed without treatment, depression with treatments, with population prevalence set at 70%, 25% and 5%, and outcome relative risks of 1.0 (ref), 2.0 and 3.0, respectively. We assumed one binary confounder with varying prevalence across depression categories and strength of association with outcome. The event incidence was assumed at 5% (among those unexposed to depression and confounder). The stage-one sample size was 88,000, with random selection of 400 in each of the three exposure categories. Across the scenarios considered relative efficiencies [i.e. Var(stage 2

MLE) / Var(SMLE)] ranged from 4 to 82, demonstrating substantial gains by utilizing exposure and outcome information in the full sample of 88,000.

As a very crude approximation to the impact of incorporating the exposure and outcome information on 88,000 women, we took an “effective sample size” approach, and assumed the worst case among the simulation scenarios considered, where the relative efficiency of the SMLE was approximately 4.0. Thus, rather than basing power calculations on the stage-two sample size of 800, we based them on 3200 (i.e. $4.0 * 800$; 1,600 in each cohort category). Under these assumptions, the minimum detectable PTD hazard ratios are significantly decreased, ranging from 1.32 to 1.38 (for PTD rate ranging from 8%-11%) in pair-wise comparisons of depression exposure/treatment categories of interest. Similarly, the minimum detectable LBW odds ratios range from 1.32 to 1.45 (for LBW rate ranging from 5% to 10%). In addition, taking the same approach to estimation of efficiency gains, the minimum detectable hazard ratio and odds ratio for effect modification by comorbidity status (yes vs. no) are 1.31 and 1.37 in analyses of PTD and LBW, respectively. We acknowledge that these estimates of gains in efficiency are based on results from a simulation study which did not reflect the complexities in analyses that this study will encounter (e.g. multiple confounders, both multicategory and continuous).

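### Aim 2's dose-level head-to-head contrasts set the comparator's dose group from Aim 1 outcome results in the same women, which biases those contrasts towards the comparator

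*Combined protocol and SAP*

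**What the plan says.** All of this is in the combined protocol and SAP, section 6.1, under Aim 2.

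- The main Aim 2 analysis is three pairwise hazard ratios among cohorts A, B and C, taken from the Cox model built for Aim 1. No dose enters.
- A second set of contrasts follows. It rests on the Aim 1 dose-response results and compares levels of one treatment with particular levels of another. The example lists three antidepressant-duration bands (under 30, 30 to 120 and over 120 days). Against them it sets a single psychotherapy level, at or above "4 visits that has shown to be effective".
- The next sentence gives the basis for that level: "We would categorize the comparator treatment (e.g., psychotherapy), based on the Aim 1 findings". Its illustration is an absence of effect below 4 visits.
- Low birthweight is to be analysed in parallel.

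Section 6.1 mentions no sample split, cross-validation, shrinkage or selection-adjusted interval for this step. Under Aim 2 the exploratory label is attached only to the analysis by depression severity. The caution about multiple comparisons in section 6.2.2 concerns the split by depression type.

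**The concern.** The Aim 1 dose-response analysis looks at PTD by number of sessions. If the session group that looks effective is then carried into Aim 2, the births that chose it are also the births that test it. Chance lows in PTD are kept and chance highs are set aside. The other treatment is shown at all its levels and gets no such advantage.

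Covariate adjustment and the propensity score analysis in section 6.1.1 deal with confounding. They cannot remove a bias that comes from using the outcome to define the group.

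At stake is a part of the answer to Aim 2 that clinicians may quote: how a given amount of one treatment compares with an effective amount of another. With no true difference, that comparison would tend to favour the comparator.

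**Working it through.** **1. Inputs from the documents (section 6.2.2).** Error rate and power: "two-sided test, significance level (α) = .05, power (1- β) =.80". Each primary contrast "can be characterized as a comparison of two groups of 400 women". The PTD rate is "ranging from 8% - 11" per cent, midpoint 9.5%. For the two-stage estimator: "rather than basing power calculations on the stage-two sample size of 800, we based them on 3200", that is 1,600 per cohort.

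**2. The plan's own figure.** The plan states: "Minimum detectable hazard ratios for PTD range from 1.69 – 1.83 across the range in expected rate of PTD". Take the rate r as the reference-group rate. Expected events are n × [r + 1 − (1 − r)^HR], and Schoenfeld power is Φ(ln HR × √(events/4) − 1.96).

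- r = 8%, HR 1.83: 400 × [0.08 + 1 − 0.92^1.83] = 88.6 events, power 0.812.
- r = 11%, HR 1.69: 400 × [0.11 + 1 − 0.89^1.69] = 115.5 events, power 0.805.
- Solved for power 0.80, the detectable HRs are 1.82 and 1.69. With 1,600 per cohort they are 1.38 and 1.32, as the plan states.

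The figures reproduce. They cover whole cohorts only; no power is given for the smaller dose groups.

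**3. Direction.** Suppose every candidate session group has the same true risk p. Each observed risk averages p, but the expected value of the smallest of them is below p. Choosing the group by its low observed risk therefore understates that risk.

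**4. Null simulation, odds-ratio scale.** Assumptions that are not in the documents: cohort B falls into four session bands of 30/30/25/15%, candidate groups are all women at or above a band, and there are no covariates. The cohort size of 733 is also assumed. PTD is 9.5% everywhere, with 20,000 replicates. The mean log odds ratio of selected B against all of A is exponentiated; below 1 favours the comparator B.

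| Rule for choosing the psychotherapy group | 400 | 733 | 1,600 |
|---|---|---|---|
| Fixed cut | 1.00 | 1.00 | 1.00 |
| Lowest-risk cut | 0.81 | 0.86 | 0.90 |
| Lowest-risk cut, top 15% band alone not allowed | 0.90 | 0.93 | 0.95 |
| Better of whole cohort and upper 40% | 0.92 | 0.94 | 0.96 |

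The lowest-risk search lands on the top band about 40% of the time. At 400 per cohort that band is 0.15 × 400 = 60 women with 60 × 0.095 = 5.7 expected events, which is why the first rule is the most biased. Two-sided error under lowest-risk selection is about 3 to 5%.

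**5. Second null simulation, hazard-ratio scale.** Different assumptions: 1 to 10 sessions, uniform or skewed to few; cuts from 2 to 8; PTD 8 to 11%; 60,000 replicates. The HR is A against selected B, so above 1 favours the comparator.

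| Rule | 400 per cohort | 1,600 per cohort |
|---|---|---|
| Whole cohorts, or 4-visit cut fixed in advance | 1.00 | 1.00 |
| 4 or more visits used only if it looks better than fewer | 1.08–1.18 | 1.04–1.09 |
| Best cut | 1.11–1.28 | 1.06–1.13 |
| Best cut, only after a significant dose trend | 1.34–1.64 | 1.16–1.39 |
| 4 or more visits, only if significant against D | 1.45–1.99 | 1.19–1.35 |

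In the last two rows the contrast falsely favours B in 14 to 35% of the studies that reach it, against a nominal 2.5%. Under the null, only about 2 to 11% of studies reach it. Averaged over all studies, best-cut selection falsely favours B in about 3 to 6%.

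**6. Scale.** At 1,600 per cohort, |ln 0.90| = 0.105 and |ln 0.96| = 0.041. The plan's detectable effects there are ln 1.32 = 0.278 and ln 1.38 = 0.322. The null bias is thus between 0.041/0.322 = 13% and 0.105/0.278 = 38% of the effect the study is sized to detect, treating odds and hazard ratios as close at this event rate.

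**The case against.** The strongest reply is that Aim 2 is defined throughout by whole cohorts. The specific aims, section 5 and the power calculation all describe it so, and those contrasts involve no dose selection. This stands. A reader might infer that the Aim 2 head-to-head result as a whole is biased, or biased towards psychotherapy. The documents support neither reading. The whole-cohort hazard ratios are 1.00 under the null. Psychotherapy is only an example, so if antidepressants were the comparator, the same step would favour antidepressants.

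A second reply is that no search for the lowest-risk cut is written down. The wording is conditional, the cuts are examples, and the sentence might mean only that the comparator is split into levels. It is true that no search rule is given, so the lowest-risk figures are one reading and not the plan's stated procedure. A harmless split, however, does not fit text that singles out a level shown to be effective and ties the categories to the Aim 1 findings. The 4-visit figure could be outside knowledge, but no source is cited and the following sentence points to Aim 1.

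A third reply concerns size. The bands and the 733 are assumed, and 400 per cohort is the pessimistic end, because session counts and dispensing are in the medical record for all stage-one women and estimation uses all 88,000. The simulations are also unadjusted, with fixed dose groups, whereas the plan adjusts for confounders and treats dose as time-dependent in Aim 1. All this is fair, and it is why a range is given. The direction was the same under every selection rule tried.

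**Conclusion.** The point holds for the dose-level contrasts of Aim 2 and for nothing wider. Followed as written, the plan uses PTD results to define the comparator's dose group and then compares that group on the same births, with no correction and no exploratory label. The estimate leans towards the comparator, and the interval does not show it.

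With no true difference, PTD at 9.5% and the assumed 30/30/25/15% bands, the odds ratio is about 0.81 to 0.90 if the lowest-risk cut is chosen and about 0.90 to 0.96 under milder rules, across 400 to 1,600 women per cohort. The selection rule, the session distribution and the cohort size are all assumptions.

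A reader might also infer a generally inflated false-positive rate. The calculations do not show that: without conditioning on Aim 1, two-sided error stays close to nominal, about 3 to 5% in the banded set-up and at most about 6% in the wider cut search, though the errors fall mostly on the comparator's side. The main harm is a biased estimate. Bias and false-positive rate are both clearly worse if the contrast is run only after a significant Aim 1 result.

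This should be changed before analysis; it does not threaten the main Aim 2 comparison.

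**What to change.** In section 6.1, Aim 2:

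- Before outcomes are examined, fix the analysis categories of dose for every treatment. The 4-visit split and the three antidepressant-duration bands already written there would serve.
- Report all levels of both treatments in the dose-level contrasts, for PTD and for low birthweight.
- Delete the sentence that sets the categories from the Aim 1 findings.
- Label any data-derived cut exploratory, and report it with a correction that repeats the selection step (bootstrap or cross-validation).

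In simulation, a cut fixed in advance, or chosen in one set of women and tested in another, gives a null hazard ratio of 1.00. The cost is a small change of text, with no new data. The drawback is that a fixed cut may not be the most informative one, which the exploratory analysis can still address.
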